6.2.1 Administration Parameters

At time of enrollment all patients will be on a stable, standard dose of lenalidomide given on days 1 – 21 of a 28 day cycle.

The following parameters must be present for each dose of the vaccine to be administered:

- No systemic infections requiring treatment
- Hemoglobin > 8g/dL
- Platelets > 20,000
- ALT/AST < 3X upper limit of normal
- Patient must be receiving lenalidomide on the day of the vaccine
- Missed vaccine doses can be made up within 2 weeks of the missed dose, with a delay by an equal number of days for the next dose (and the remaining doses), for the first 4 vaccine doses (there will be a minimum of one month between doses).
- Vaccine doses that are missed beyond the 4th dose of vaccine, can be made up within 1 month of the original date of administration. Subsequent doses do not need to be delayed.

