6.4.17 General Concomitant Medication and Supportive Care Guidelines

Because there is a potential for interaction of lenalidomide with other concomitantly administered drugs, the case report form must capture the concurrent use of all other drugs, over-the-counter medications, or alternative therapies.

The allogeneic myeloma K562/GM-CSF vaccine is an immune based treatment. As such, immunosuppressants in the form of steroids, cyclosporine, imuran, cellcept, sirolimus, tacrolimus and others should not be administered during this clinical trial. For questions, address the Primary Investigator.

65 Duration of Follow-up

Patients will be followed for a minimum of 36 months after enrollment in the study or until relapse or death, whichever occurs first. Patients removed from study treatment for unacceptable adverse events will be followed until resolution or stabilization of the adverse event.

66 Dose delay/Dose modifications

There are no dose modifications for the vaccine. Lenalidomide dose adjustments as noted in section **6.4.13**.

NCI CTC Toxicity Grade (CTC AE 4.0)	Dose Modification Instructions
Grade 3 neutropenia associated with fever (temperature $\geq 38.5^{\circ}\text{C}$) or Grade 4 neutropenia	
 Hold (interrupt) lenalidomide dose. Follow CBC weekly. If neutropenia has resolved to \leq grade 2, restart lenalidomide at next lower dose level and continue through the scheduled end of the cycle. Otherwise, omit for remainder of cycle and reduce the dose of lenalidomide by 1 dose level at the start of the next cycle. Omitted doses are not made up.
Thrombocytopenia \geqGrade 3 (platelet count $< 50,000/\text{mm}^3$)	
 Hold (interrupt) lenalidomide dose. Follow CBC weekly. NOTE: Consider criteria (perhaps based on platelet count) for holding and then resuming prophylactic anti-coagulation, if applicable. If thrombocytopenia resolves to \leq grade 2, restart lenalidomide at next lower dose level and continue through scheduled end of the cycle. Otherwise, omit for remainder of cycle and reduce the dose of lenalidomide by 1 dose level at start of next cycle. Omitted doses are not made up.
Non-blistering rash	

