Tumor immunology assessments will be made at baseline and on day 14 of cycles 3, 6, and 12 (the 1-year assessment). At each time point, graphical (e.g. boxplots over time, spaghetti plots) and numeric (e.g. median, range, proportion) summaries will be used to explore the continuous (e.g. T cell populations) and binary (e.g. tumor specific immunity) outcomes. If appropriate, transformations (e.g. log) will be used to address skewness in the data. Cross-sectional comparisons will be made using t-tests, Kruskal-Wallis tests, or linear regression and Chi-squared tests, Fisher’s exact test, or logistic regression for continuous and categorical outcomes, respectively. Generalized estimating equations and mixed effects models will be used to formally model the behavior over time and compare treatment groups and/or risk factors while adjusting for repeated measurements within each individual. The association between baseline tumor measurement as well as changes in tumor measurements over time and clinical outcomes will be assessed using Cox proportional hazards models.

Toxicity will be scored using NCI CTC Version 4.0 for toxicity and adverse events. All toxicities will be summarized overall, by treatment group, and within subgroups of interest (e.g. true CR status, MM type). The number of toxicities and number of affected patients will be tabulated by type, grade, and relatedness to study treatment (overall and for each treatment). In addition to counts and proportions, the toxicity rates will be modeled and compared between treatment groups and subgroups of interest using Poisson regression or Negative Binomial regression, as appropriate.

11.3 Toxicity Stopping Guidelines:

The proportion of unacceptable toxicities will be continuously monitored in each arm separately. Unacceptable toxicities include hematologic toxicities of lenalidomide: low neutrophils (ANC <1000) and low platelets (<50K), for which we would hold the vaccine administration, as well as vaccine related toxicities which include: grade 3/4 local reactions (erythema, swelling, pain) and systemic symptoms (fevers, rash) (Refer to **7.6.1** and **7.6.2** for guidelines on attribution of toxicities).

Unacceptable toxicities as scored using **NCI CTCAE V5.0** include:

- Any laboratory or clinical organ dysfunction \geq Grade 3
- Abnormalities of coagulation (prolonged prothrombin, partial thromboplastin and clotting times \geq Grade 3)
- Autoimmune disease reactivation or development \geq Grade 2

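### The per-dose vaccine checklist in 6.2.1 has no neutrophil criterion, although 11.3 says vaccine is held at ANC below 1000; the platelet limits also differ on paper, and neither section cites the other

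*Combined protocol and SAP*

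**What the plan says.** Three sections of the combined protocol and SAP bear on whether a patient with low counts is vaccinated.

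- **6.2.1 Administration Parameters** opens its list with "The following parameters must be present for each dose of the vaccine to be administered". The laboratory items are "Hemoglobin > 8g/dL", "Platelets > 20,000" and a transaminase limit. There is also an infection item and the condition "Patient must be receiving lenalidomide on the day of the vaccine". No item concerns neutrophils.
- **11.3 Toxicity Stopping Guidelines** lists haematologic toxicities of lenalidomide among the unacceptable toxicities and attaches a vaccine hold to them: "low neutrophils (ANC <1000) and low platelets (<50K), for which we would hold the vaccine administration".
- **6.6 Dose delay/Dose modifications** states that the vaccine has no dose modifications and gives count-based rules for lenalidomide only. Lenalidomide is interrupted for grade 3 or worse thrombocytopenia, which the table equates with platelets below 50,000. For neutrophils the triggers are "Grade 3 neutropenia associated with fever" (38.5°C or higher) and grade 4 neutropenia.

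Section 6.2.1 does not mention a hold in 11.3, and 11.3 does not mention the checklist in 6.2.1.

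**The concern.** The rule for giving or withholding an injection appears in two places with different content. The place where a person preparing to give a dose would naturally look is 6.2.1, under vaccine administration. The ANC hold appears only in a subordinate clause of the biostatistics section. Someone who works through 6.2.1 faithfully could inject a patient whom 11.3 describes as held.

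Two things are at stake. The first is dosing-day safety, since the protection that 11.3 describes is not built into the per-dose check. The second is consistency of exposure. With 18 patients per arm, doses given or missed according to which section was consulted add avoidable variation, and it is unclear whether an injection at ANC below 1000 is a protocol deviation. Section 11.3 also gives no count at which a held vaccine may resume, although 6.2.1 limits make-up doses to 2 weeks for the first four doses and 1 month after that.

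**Working it through.** No formula applies and the plan gives no figure to reproduce. The check is to take each blood-count state, assume that every other 6.2.1 item is met, and follow it through the three sections.

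| Count on the vaccine day | 6.2.1 count item | Lenalidomide under 6.6 | 6.2.1 lenalidomide item | 11.3 | Do the sections agree? |
|---|---|---|---|---|---|
| ANC below 1000, afebrile, not grade 4 | none exists | continues | met | hold | **No** |
| ANC below 1000, grade 3 with fever or grade 4 | none exists | interrupted | not met | hold | Yes, indirectly |
| Platelets above 20,000 and below 50,000 | met | interrupted | not met | hold | Yes, indirectly |
| Platelets 20,000 or lower | not met | interrupted | not met | hold | Yes |

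**Neutrophils.** The first row is the gap. I looked for other text that might close it and found none:

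- The ANC criterion above 1000 in 7.1 applies at entry, not at each dose.
- Section 6.2.3 lists reasons to discontinue treatment, not reasons to hold a single dose.
- Sections 6.2 and 6.6 say that the vaccine has no dose modification and do not point to 11.3.
- The infection item in 6.2.1 concerns infections requiring treatment, not a low count.

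**Platelets.** In the third row the written limits differ (20,000 against 50,000), but the outcome is the same when 6.6 and the lenalidomide item are applied together. Lenalidomide restarts only when thrombocytopenia is back to grade 2 or better. The protection is indirect: it depends on the lenalidomide interruption being made and recognised before the injection. Hence the 20,000 item is mostly redundant rather than a second open gap.

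**Toxicity count.** Section 11.3 classes ANC below 1000 and platelets below 50K as unacceptable toxicities in themselves. Their contribution to the count against Table 11.1 does not depend on whether the injection was given.

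**The case against.** The best defence is that 6.2.1 states necessary conditions and never says that they suffice. On that reading 11.3 adds a further condition, and a site can comply with both by withholding vaccine whenever either section says so. Logically this is sound, and it means that the two sections can be obeyed together. The documents do not state this reading, however. There is no cross-reference in either direction, and a per-dose list that includes haemoglobin, platelets and transaminases looks complete to its user. What stands of the objection is that this is a failure of coordination between sections, fixable in text, and not a pair of instructions that cannot both be followed.

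A reader might also infer three stronger things that the documents do not support.

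- *That patients with platelets between 20,000 and 50,000 would be vaccinated against 11.3.* The lenalidomide interruption in 6.6, with the lenalidomide item in 6.2.1, largely prevents this.
- *That the stopping rule would count differently depending on which section is followed.* It would not, because 11.3 counts these cytopenias regardless of vaccination.
- *That several patients per arm would be affected.* Section 4.2 cites 41.2% grade 3 or 4 neutropenia in a lenalidomide trial, and halving it gives 0.5 × 0.412 × 18 = 3.7 per arm. That figure has no footing. It includes the grade 4 and febrile cases for which lenalidomide would already be interrupted. It is a rate over a trial with median follow-up of 17.6 months, whereas the gap matters only if the low count falls on one of the vaccine days (months 1, 2, 3, 6, 12, 24 and 36 in the 6.1 schema). It comes from relapsed or refractory patients also taking dexamethasone, while patients here are in remission, off steroids and established on lenalidomide. The factor of one half has no source.

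**Conclusion.** The point holds for neutrophils. An afebrile patient with ANC below 1000 that is not grade 4 satisfies 6.2.1 in full, while 11.3 says vaccine is held, and nothing else in the protocol resolves it. For platelets, the thresholds are inconsistent on paper with little expected effect on who is injected, provided that 6.6 and the lenalidomide item are both applied.

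The size can be given only as the range of counts affected. The documents report no neutropenia rate for patients like these on vaccine days, so the number of doses involved cannot be estimated. The conclusion rests on the text of the three sections as they stand and on taking the 6.2.1 list as the operative check before each dose, which its opening words support. It implies no error in the stopping boundaries or their operating characteristics. It should be corrected because it concerns a dosing-day safety rule and the correction is simple.

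**What to change.** Reconcile 6.2.1, 6.6 and 11.3 so that a single section sets the haematologic criteria for giving or holding vaccine, and have the other two cite it. That section should state whether a neutrophil criterion applies at each dose, use one platelet criterion, and say how a hold ends and how it fits the make-up windows in 6.2.1. It should also say whether the listed conditions are sufficient or only necessary. The sponsor and investigator must decide the values; this review takes no position on them.

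The cost is a short protocol amendment. CBC with differential is already in the schedule of assessments at the vaccine visits, so no visit, sample or procedure is added, and the sample size and the stopping tables are unaffected if the toxicity definitions in 11.3 are left as they are. If reconciliation changes those definitions, the expected rate and the 30% threshold behind Table 11.1 should be re-read against the new definition.

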6 INVESTIGATIONAL PLAN

6.1 Overall design:

[figure not shown]
Patients with newly diagnosed or relapsed/refractory multiple myeloma (NDMM or RMM) in CR or nCR who meet appropriate criteria will be eligible for enrollment.

Specifically:

[figure not shown]
- Patients with NDMM who have completed 6 cycles of treatment with any lenalidomide containing regimen (e.g. KRD, VRD, Rd, BiRD or R alone) and who have been in CR or nCR for ≥ 3 months.
- Patients with MM who have undergone ASCT will only become eligible ≥ 12 months following date of cell infusion, will have been on lenalidomide maintenance for ≥ 6 cycles prior to enrollment, and continue to meet criteria for CR or nCR for ≥ 3 months.
- Patients with RMM will need to have completed at least 6 cycles of current therapy with a lenalidomide containing regimen, and be in CR or nCR for ≥ 3 months.
- All patients must be MRD positive at 10^{-4} by NGS sequencing at enrollment

Eligible patients who go on to enroll will be randomized in a 1:1:1 fashion to one of three arms. All patients will continue on a standard dose of lenalidomide (15mg daily, to be adjusted as clinically necessary), given on days 1 – 21 of a 28 day cycle. Patients on the myeloma vaccine arm will receive injections with an allogeneic myeloma vaccine administered intradermally on day 14 of cycles 1, 2, 3, 6 and annually for a minimum of 36 months in addition to lenalidomide unless otherwise clinically indicated, or until progression. Patients on myeloma plus Prevnar vaccine arm will receive injections of both allogenic myeloma vaccine, intradermally, and Prevnar vaccine, intramuscularly, on day 14 of cycles 1, 2, 3, 6, and annually for a minimum of 36 months in addition to lenalidomide unless otherwise clinically indicated, or until progression. Patients on the myeloma vaccine placebo arm will receive myeloma vaccine placebo on the same schedule as allogeneic myeloma vaccine. If assigned to either of the two arms that do not include Prevnar, then patients will receive placebo in lieu of Prevnar on the same schedule. The placebo will be saline. The study schema is shown below:

SCHEMA

Vaccination Schedule

Allogeneic Myeloma Vaccine or placebo administration – in months: 1, 2, 3, 6, 12, 24, and 36
 Prevnar or Prevnar placebo administration – concurrent with myeloma vaccine administration
 MRD testing – enrollment, 6 mo, 12 mo, annually for the duration of study

6789

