11 BIOSTATISTICAL ANALYSIS

11.1 Sample Size Considerations

The primary endpoint of this phase II study is progression free survival (PFS). The primary analysis will compare the control arm (lenalidomide plus placebo) versus the pooled allogenic myeloma vaccine arms (with and without Prevnar). In a prior study, the median PFS for patients on Len containing therapy was 17.9 months. Patients will be accrued over the course of 2 years with a minimum follow-up of 3 years (i.e. all patients will have 3-5 years of follow-up). A sample size of 54 patients (18 placebo vs 36 allogenic myeloma) would provide 80% power to detect an increase in the median PFS from 18 months in the control arm to 42.8 months in the pooled vaccine arm ($HR = 0.4199$) based upon a log-rank test assuming a two-sided type I error rate of 10% and a loss to follow-up rate of 1% per year (5% overall). The accrual rate is expected to be 2.3 per month. Due to the small sample size, no interim efficacy analysis is planned at this time.

Our principal secondary endpoints will be conversion from “near CR” (M-spike at or below 0 but IFE positive), to “true CR” (IFE negative), and conversion from MRD positive status to MRD negative status. The trial will accrue patients for a total $n=18$ per arm at single center for a period two years, while trial duration for every patient enrolled will be 3 years. The analysis will be performed on the intention to treat population.

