- Immune system disorders including myalgias or headaches \geq Grade 3
- Immune system disorders including allergic or hypersensitivity reactions such as rash, or fever \geq Grade 3
- Immune system disorders including anaphylaxis or anaphylactoid reactions (eg. Wheezing, urticarial, hypotension) \geq Grade 3
- General disorders and administration site conditions including injection site reactions such as tenderness with or without associated symptoms (e.g., warmth, erythema, itching, and malaise) \geq Grade 3
- Any other undefined or unanticipated adverse event \geq Grade 3
- Any death on study

If the levels of unacceptable toxicities is too high (i.e. a high probability that they exceed the maximum threshold of 30%), then enrollment will be suspended pending review by the PI, DSMB, and Celgene. Any death on study within 30 days of GVAX administration will lead to suspension of enrollment pending review by the PI, DSMB, and Celgene.

A Bayesian stopping guideline will be used to assess the level of unacceptable toxicity. We expect the rate of unacceptable toxicities to be 25%. Hence a Beta(1, 3) prior was used. After the first three patients are recruited, toxicity will be monitored continuously. Accrual will be suspended if the probability that the unacceptable toxicity rate exceeds 30% is 0.70 or higher. Table 11.1 shows the number of toxicities needed to halt accrual.

Table 11.1. The number of toxicities needed to trigger stopping guidelines throughout the course of the study.

Number of Subjects Per Treatment Arm	Number of toxicities needed to trigger re-evaluation
3-4	3
5-7	4
8-10	5
11-13	6
14-16	7
17-18	8

The operating characteristics of these stopping guidelines were generated based upon 5000 simulations (Table 11.1).

Table 11.2. Probability of triggering stopping guidelines based upon range of underlying toxicity rates.

True Toxicity (DLT) Risk	Prob. Declare Treatment Too Toxic	Avg. Sample Size
0.05	<0.1%	18.0
0.10	0.4%	18.0
0.15	2.7%	17.7
0.20	7.6%	17.2
0.25	15.2%	16.5
0.30	27.7%	15.4
0.35	44.0%	13.8
0.40	59.5%	12.3
0.45	74.2%	10.7

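### The toxicity stopping rule sets no evaluation window and does not say when a patient enters the denominator, so Table 11.2, which assumes immediate outcomes, does not describe it under staggered accrual

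*Combined protocol and SAP*

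**What the plan says.** Section 11.3 monitors unacceptable toxicity in each arm separately. On the start of monitoring it says "After the first three patients are recruited, toxicity will be monitored continuously". The prior and criterion are given as "We expect the rate of unacceptable toxicities to be 25" percent, "Hence a Beta(1, 3) prior was used" and "Accrual will be suspended if the probability that the unacceptable toxicity rate exceeds 30% is 0.70 or higher". Table 11.1 gives the number of toxicities that prompts re-evaluation, indexed by "Number of Subjects Per Treatment Arm": 3 at 3-4 subjects, 4 at 5-7, 5 at 8-10, 6 at 11-13, 7 at 14-16 and 8 at 17-18. Table 11.2 is titled "Probability of triggering stopping guidelines based upon range of underlying toxicity rates" and comes from 5000 simulations whose toxicity timing is not described.

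The qualifying events include organ dysfunction and any other adverse event of grade 3 or more, and any death on study. The only time window in 11.3 is 30 days after vaccination, for a separate rule on deaths.

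Other sections bear on timing. Section 6.1: "Patients on the myeloma vaccine arm will receive injections with an allogeneic myeloma vaccine administered intradermally on day 14 of cycles 1, 2, 3, 6". Yearly injections follow, which section 6.2.3 takes through 36 months. Section 11.1: "The accrual rate is expected to be 2.3 per month". Section 10.1 makes a patient evaluable for safety once any study treatment, lenalidomide included, has started, and section 7.1 requires all patients to be on lenalidomide at screening. Section 11.2 instead limits the safety population to patients with at least one dose of assigned treatment.

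**The concern.** A rule of the form x toxicities among n patients has known properties only when every one of the n has been observed for the period to which the rate refers. Section 11.3 gives no such period. On its most natural reading a patient joins the denominator at recruitment, about two weeks before the first injection, and sits there without an event until one occurs. Patients who are not yet exposed, or only partly exposed, then dilute the observed rate.

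What is at stake is the protection that Table 11.2 appears to promise. At a true risk of 45% it states a 74.2% chance of declaring the arm too toxic, after an average of 10.7 patients. The consequence of a trigger is suspended enrollment. A trigger that fires after the arm is full protects nobody from being enrolled in that arm.

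**Working it through.** **Inputs from the documents.** Table 11.1 boundaries, 18 patients per arm, monitoring from n = 3, the Beta(1,3) prior with cutoff 0.70 (all section 11.3), and 2.3 patients per month in total (section 11.1). Per arm that is 2.3/3 = 0.77 per month, or one patient every 3/2.3 = 1.3 months.

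**Assumptions, not in the documents.** Onset is uniform over a stated interval after recruitment; arrivals are Poisson; each affected patient has one event; the Table 11.2 risk is the patient's eventual risk.

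**Step 1: reproduce Table 11.2.** Exact binomial path calculation for n = 3 to 18 with Table 11.1 boundaries, each outcome known before the next patient is counted. Average n is the number enrolled at the trigger, or 18 if there is none.

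| True risk | Stated trigger (avg n) | Exact, immediate outcomes (avg n) |
|---|---|---|
| 0.25 | 15.2% (16.5) | 16.1% (16.4) |
| 0.30 | 27.7% (15.4) | 28.6% (15.3) |
| 0.40 | 59.5% (12.3) | 59.6% (12.3) |
| 0.45 | 74.2% (10.7) | 73.8% (10.7) |

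Agreement is within one percentage point, so the table assumes no delay between entry and outcome.

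**Step 2: staggered entry and delayed onset.** Monte Carlo simulation with the same boundaries. Patients count from recruitment and toxicities count at onset.

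| True risk | Onset after recruitment | Trigger ever | Trigger before 18th patient | Avg n |
|---|---|---|---|---|
| 0.45 | 0.5-1.5 months | about 71% | about 67% | 11.7 |
| 0.45 | 0.5-6.5 months | about 65% | about 50% | 14.3 |
| 0.30 | 0.5-1.5 months | about 25% | about 23% | 15.9 |
| 0.30 | 0.5-6.5 months | about 19% | about 14% | 17.0 |

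With a very long delay all 18 patients are enrolled before the events arrive. The chance of ever triggering then falls to P(X ≥ 8 of 18), which is 14.1% at a risk of 0.30 and 60.9% at 0.45, almost all of it after the arm is full.

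**Step 3: does the written criterion give Table 11.1?** After x events in n patients the posterior is Beta(1 + x, 3 + n − x). For 2 of 3, P(rate > 0.30) = 0.744, which already meets 0.70, but the table requires 3. For 7 of 18 it is 0.723, but the table requires 8. Over the whole range the written criterion gives 2 at n = 3, 3 at 4-6, 4 at 7-9, 5 at 10-12, 6 at 13-15 and 7 at 16-18. With onset at 0.5-6.5 months that boundary triggers in about 81% at a risk of 0.45 and about 35% at 0.30, above the stated 74.2% and 27.7%.

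**Step 4: two other readings.**
- *Tabled risk as a 6-month risk, constant hazard, events counted to 36 months.* A 10% rate becomes 1 − 0.9^6 = 47%, and the rule eventually triggers in 66.8% (stated 0.4%), though in only 2.7% before the 18th patient. A 25% rate becomes 1 − 0.75^6 = 82%; the rule triggers in about 100% eventually and in 50.9% before the 18th patient (stated 15.2%).
- *Toxicities counted rather than affected patients.* Assume a 30% chance of a second event per affected patient, Table 11.1 boundaries and onset at 0.5-6.5 months. Triggering is about 32% at a risk of 0.25 and 87% at 0.45, against 15.2% and 74.2%.

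**The case against.** The strongest reply has four parts.

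1. *No sentence says that a recruited patient counts as event-free.* True. Section 11.2 can be read as admitting a patient only after a first assigned dose, while section 10.1 points the other way. This leaves the denominator ambiguous, which is part of the point. Entry at first dose would not supply an evaluation window either.

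2. *The likely toxicities are early.* Section 6.2.4 describes local reactions of about a week and GM-CSF detectable for 3-5 days. If unacceptable toxicity follows the first injection closely, the loss in overall trigger probability is about 3 percentage points at either risk. This stands. But the qualifying list is much wider than injection reactions, and three of the first four injections come after cycle 1.

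3. *The direction is not fixed.* A reader might infer that the rule always errs in the unsafe direction. The documents do not support that: steps 3 and 4 give three readings under which it triggers more often than stated. A reader might also infer that a time-weighted denominator with the existing boundaries repairs the rule. With a 6.5-month window and rounding to the nearest integer, it gives about 15% at a risk of 0.25 when onset is spread over 0.5-6.5 months, but about 22-23% when onset is at 0.5-1.5 months. The match with Table 11.2 depends on the onset assumption.

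4. *There are other safeguards.* Any death within 30 days of vaccination suspends enrollment, safety is monitored continuously, and the DSMB reviews toxicity at least annually and may recommend ending accrual. These soften the consequence but do not make Table 11.2 a description of the rule.

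**Conclusion.** The concern holds as a gap in definition with a measurable consequence. Section 11.3 leaves the evaluation period and the entry to the denominator open, and Table 11.2 rests on immediate outcomes that staggered accrual and injections to 36 months cannot deliver.

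Under Table 11.1 boundaries, counting from recruitment and an eventual per-patient risk, the chance of a trigger before the arm is full at a risk of 0.45 is about 67% for early onset and about 50% for onset spread to 6.5 months, against 74.2% stated for any trigger. Average enrollment is 11.7 and 14.3 against 10.7. These sizes rest on assumed onset times. With a short-period risk, repeat events or the written 0.70 criterion, the rule can trigger more often than stated. What is certain is that the stated figures refer to no defined period; the sign and size of the error depend on choices that the plan has not made. This should be corrected, but it does not by itself make the trial unsafe.

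**What to change.** In section 11.3:

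1. Reconcile Table 11.1 with the written Beta(1,3) and 0.70 criterion, so that there is one boundary.
2. State one evaluation window, and say that the 25% expected rate, the 30% threshold and the Table 11.2 risks all refer to it.
3. Count patients with at least one unacceptable toxicity, not toxicities.
4. State when a patient enters the denominator and how incomplete follow-up is handled, for example by weighting each event-free patient by the fraction of the window completed, with the rounding rule given.
5. Re-simulate Table 11.2 at 2.3 patients per month under a range of onset times. Report the trigger probability before the arm is full beside the overall probability and average sample size.
6. Say that events after the window stay under continuous safety monitoring and DSMB review.

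The cost is a paragraph and a re-simulation, with no extra patients or procedures. Some Table 11.2 figures will look less favorable, and counting patients instead of events lowers triggering where patients have repeat events, so the boundary should be checked after that choice is made.

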10.2.2 Data Safety Monitoring Board (DSMB)

The role of the DSMB will be to monitor the study for safety and toxicity issues regarding the combination of Lenalidomide with a cellular myeloma vaccine. Interim analysis of toxicity, outcome, and ongoing scientific investigations will be performed at least annually by the Sidney Kimmel Comprehensive Cancer Center Data Safety Monitoring Board (SKCCC DSMB). The SKCCC DSMB Recommendation letter will state the timeline for the next required review. The SKCCC DSMB will review aspects of this trial that are outlined in the responsibilities section of the Data and Safety Monitoring Board (DSMB) Guidance. If the committee decides that amendments should be made to this trial, recommendations will be made in writing to the study Principal Investigator. The study team will submit modifications to the IRB within 60 days of receipt from the DSMB. The Associate Director of Clinical Research will arbitrate any disagreements between the DSMB and the study Principal Investigator. These changes may include early termination of accrual if deemed appropriate.

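### Table 11.1 does not follow from the stated Beta(1,3) and 0.70 rule: it needs one more toxicity at 11 of 16 arm sizes, and Table 11.2 describes the table, not the rule

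*Combined protocol and SAP*

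**What the plan says.** Section 11.3 (Toxicity Stopping Guidelines) monitors each arm separately. It expects a 25% rate of unacceptable toxicity and sets 30% as the maximum. The rule is fixed in consecutive sentences:

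- Prior: "Hence a Beta(1, 3) prior was used".
- Looks: "After the first three patients are recruited, toxicity will be monitored continuously".
- Decision: "Accrual will be suspended if the probability that the unacceptable toxicity rate exceeds 30% is 0.70 or higher".
- Link to the table: "Table 11.1 shows the number of toxicities needed to halt accrual".

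Table 11.1 then gives 3 toxicities at 3-4 patients per arm, 4 at 5-7, 5 at 8-10, 6 at 11-13, 7 at 14-16 and 8 at 17-18.

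On Table 11.2 the section says: "The operating characteristics of these stopping guidelines were generated based upon 5000 simulations". (The cross-reference there points to Table 11.1, but the results are in Table 11.2.) Table 11.2 gives, for example, a 15.2% probability of triggering and an average of 16.5 patients at a true rate of 25%, and 27.7% and 15.4 at 30%.

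Two other safeguards stand beside this boundary. One is in the same section: "Any death on study within 30 days of GVAX administration will lead to suspension of enrollment pending review by the PI, DSMB, and Celgene". The other is in section 10.2.2: "Interim analysis of toxicity, outcome, and ongoing scientific investigations will be performed at least annually".

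**The concern.** A beta prior, a threshold and a posterior cut-off determine the boundary completely, so Table 11.1 can be checked directly. It appeared too permissive. Two toxicities in the first three patients already move a Beta(1,3) prior well above the 30% mark, yet the table asks for three.

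This is the plan's only quantitative boundary on the toxicity rate. If the sentence and the table disagree, the PI, the DSMB and Celgene hold two versions of it and could reach opposite decisions on suspending enrollment from the same data. The published operating characteristics can describe only one of the two.

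**Working it through.** **Inputs**, all from section 11.3 except the arm size of 18 (Synopsis and section 11.1): prior Beta(1,3), threshold 0.30, cut-off 0.70, a look after every patient from the 3rd to the 18th in an arm, and 5000 simulations.

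**Boundary.** After x toxicities in n patients the posterior is Beta(1+x, 3+n−x). The rule suspends at the smallest x with P(rate > 0.30) ≥ 0.70. For integer parameters, P(Beta(a,b) > 0.30) = P(Bin(a+b−1, 0.30) ≤ a−1), so one case can be done by hand. With n = 3 and x = 2 the posterior is Beta(3,4), and P(Bin(6, 0.30) ≤ 2) = 0.1176 + 0.3025 + 0.3241 = 0.744. This exceeds 0.70, so the text suspends at 2 of 3, where Table 11.1 requires 3.

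All sizes:

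| n | Table 11.1 | Stated rule | Posterior at one fewer than Table 11.1 |
|---|---|---|---|
| 3 | 3 | 2 | 0.744 |
| 4 | 3 | 3 | 0.647 |
| 5 | 4 | 3 | 0.806 |
| 6 | 4 | 3 | 0.730 |
| 7 | 4 | 4 | 0.650 |
| 8 | 5 | 4 | 0.790 |
| 9 | 5 | 4 | 0.724 |
| 10 | 5 | 5 | 0.654 |
| 11 | 6 | 5 | 0.781 |
| 12 | 6 | 5 | 0.722 |
| 13 | 6 | 6 | 0.660 |
| 14 | 7 | 6 | 0.775 |
| 15 | 7 | 6 | 0.722 |
| 16 | 7 | 7 | 0.666 |
| 17 | 8 | 7 | 0.772 |
| 18 | 8 | 7 | 0.723 |

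The two differ at n = 3, 5, 6, 8, 9, 11, 12, 14, 15, 17 and 18, always by one. They agree at 4, 7, 10, 13 and 16.

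**Operating characteristics.** These come from an exact binomial recursion over n = 1 to 18, stopping at the first crossing from n = 3 onward. Average n counts patients in the arm at crossing, or 18 if the boundary is never crossed. The Table 11.1 column is the attempt to reproduce the plan's own figures. Each z is (stated − exact P)/√(P(1−P)/5000).

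| True rate | Table 11.2 as stated: P, avg n | Exact for Table 11.1: P, avg n | z | Exact for stated rule: P, avg n | z |
|---|---|---|---|---|---|
| 0.05 | <0.1%, 18.0 | 0.06%, 18.0 | n/a | 0.9%, 17.9 | n/a |
| 0.10 | 0.4%, 18.0 | 0.65%, 17.9 | −2.2 | 4.0%, 17.5 | −12.9 |
| 0.15 | 2.7%, 17.7 | 2.7%, 17.7 | −0.1 | 10.2%, 16.7 | −17.5 |
| 0.20 | 7.6%, 17.2 | 7.5%, 17.2 | 0.2 | 20.1%, 15.6 | −22.1 |
| 0.25 | 15.2%, 16.5 | 16.1%, 16.4 | −1.8 | 33.5%, 14.1 | −27.4 |
| 0.30 | 27.7%, 15.4 | 28.6%, 15.3 | −1.4 | 48.8%, 12.5 | −29.8 |
| 0.35 | 44.0%, 13.8 | 43.8%, 13.9 | 0.3 | 63.9%, 10.8 | −29.4 |
| 0.40 | 59.5%, 12.3 | 59.6%, 12.3 | −0.1 | 77.1%, 9.1 | −29.6 |
| 0.45 | 74.2%, 10.7 | 73.8%, 10.7 | 0.7 | 87.0%, 7.7 | −26.9 |

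Table 11.2 is thus reproduced from Table 11.1 to within simulation error, and cannot have come from the rule in the text.

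**Simple explanations tried.**

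- *Strict or non-strict inequality.* No posterior equals 0.70, and the lowest value among the 11 discrepant sizes is 0.722, so the choice makes no difference.
- *A uniform shift of one.* Five sizes agree, which rules this out.
- *A different toxicity threshold.* With Beta(1,3) and 0.70, thresholds of 0.25, 0.33 and 0.35 leave 16, 2 and 3 mismatches.
- *A different prior or cut-off.* Several pairs reproduce Table 11.1 exactly: Beta(1,3) with a cut-off above 0.806 and up to 0.818; Beta(3,9) or Beta(1,5) with 0.70; Beta(2,6) or Beta(1,4) with 0.75. The documents mention none of them, so they show only that a misreported parameter could explain the mismatch.

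**The case against.** The case for a lower grade is reasonable. Crossing the boundary pauses enrollment for a review; it does not end the trial or stop treatment, and the heading of Table 11.1 speaks of re-evaluation. The gap is one toxicity per arm, and none at five sizes. Safety is also watched throughout (section 10.1), the DSMB reviews at least yearly, and early deaths have their own trigger. Staff would most naturally use the printed counts, and for those counts Table 11.2 is right. On that reading the only error is a misstated prior or cut-off.

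Much of this is true, but it does not settle the matter. Nothing in the documents says that the table overrides the sentence, and the sentence makes suspension mandatory. The other safeguards do not set a toxicity-rate boundary and do not say which of the two versions governs. That the table was the intended rule is plausible, but it is inference. The objection bears on practical risk and leaves the contradiction in place.

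**Conclusion.** The concern holds and should be corrected. Table 11.1 is not the boundary that the stated prior and cut-off produce: it is one toxicity more lenient at 11 of 16 arm sizes and equal at the other five. At the protocol's expected 25% rate, the written rule would suspend an arm about twice as often as Table 11.2 reports (33.5/15.2 = 2.2). At the 30% limit the ratio is 48.8/27.7 = 1.8.

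The boundary comparison needs only the stated prior, threshold and cut-off. The operating characteristics also assume independent patients with a common toxicity rate, each outcome known before the next look, and no resumption after a crossing. The close match to Table 11.2 under the printed counts supports that set-up. Which rule the sponsor meant cannot be told from the documents.

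**What to change.** The sponsor should confirm the intended rule, then make the prior, the cut-off, Table 11.1 and both columns of Table 11.2 agree with it.

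- **If the written rule stands**, replace Table 11.1 with 2 (n = 3), 3 (4-6), 4 (7-9), 5 (10-12), 6 (13-15) and 7 (16-18), and replace Table 11.2 with the stated-rule values in the working above.
- **If the tables stand**, correct the stated prior or cut-off to the pair actually used to generate them, taken from the original program. It should not be picked from the candidates above because it happens to fit.

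Either way, state that the text and the table are the same rule, and correct the cross-reference for the simulation results to Table 11.2. The cost is one corrected sentence or a regenerated pair of tables. No patients or procedures are added.
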